#### 10.4.7 PLANNED INTERIM ANALYSES

- Per the DSMB charter, there is a single, formal interim analysis planned after 50% patients are accrued. NO formal stopping rules have been established, given the small sample size. Rather, the DSMB will issue recommendations on halting the trial early, only for safety reasons, based on the totality of data reviewed.

### 10.5 SAMPLE SIZE

Our preliminary data suggest that 25% of patients in the usual care arm will have < 15 B lines at the conclusion of ED AHF management. With 59 patients in each of the two arms, we will have 81% power to detect an effect size of 2 (i.e. 25% in the usual care versus 50% in the strategy care), where the type I error rate is controlled at 0.05 (two-sided). Considering a conservative 10% drop-out rate, we will need a total of 130 subjects.

### 10.6 MEASURES TO MINIMIZE BIAS

---

#### 10.6.1 ENROLLMENT/ RANDOMIZATION/ MASKING PROCEDURES

Each site will be provided a block randomization table with variable block sizes of 2, 4, and 6. The data coordinating center will continuously monitor the recruitment until the targeted sample size is reached. We will utilize the REDCap Randomization module for web-based randomization.

Due the nature of the intervention and the clinical setting, this is an unblinded trial.

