#### 7.3.1 SCREENING

A signed and dated informed consent form will be obtained before any study-specific screening procedures are performed. Results of evaluations obtained as part of routine medical care, which are performed prior to obtaining informed consent, may be used in place of the protocol-specified evaluations. Patients will acknowledge and agree to the use of this information for the study by giving informed consent.

At the Baseline Visit, patients will be assigned by the Internet Web-based Randomization System (IWRS) a unique permanent identification number (referred to as the patient identification number) such that all randomized patients from each center are given consecutive identification numbers by the IWRS in successive order of inclusion. We will utilize the REDCap randomization module. (NOTE: thus each patient will have two ID's – 1) generated by IWRS and 2) blood specimen label)

Prospective study patients will have presented to the hospital for urgent therapy for AHF. Potential patients will be identified either en route to or upon arriving at the ED/hospital. Routine assessments associated with usual patient care may be used for the purposes of screening and may be completed in any order. Study specific procedures must be completed only after Informed Consent is obtained.

Randomization will occur within three hours of patient's arrival to a room within the ED where they can be seen by a physician or the first time AHF treatment is given. Waiting room time does not count against these three hours.

The following procedures will be performed prior to or during Screening:

- Obtain written informed consent (must be performed as the first study-specific procedure)
- Review of prior medical history
- Review of prior and concomitant medications
- Physical examination (including height and weight when reasonably possible)
- Vital signs measurements (includes systolic and diastolic blood pressures, heart rate, body temperature, oxygen saturation reading and respiratory rate)
- 12-Lead Electrocardiogram
- Chest X-Ray (this is not a requirement however, for inclusion)
- Blood collection for local laboratory tests, including BNP or NT-proBNP, and pregnancy test if applicable.
- Inquiry about Adverse events

---

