### 7.3.2 ENROLLMENT/BASELINE

Patients who continue to fulfill all of the inclusion/exclusion criteria will be randomized no later than 3 hours after the first recorded time stamp when patient placed in a room to be seen by a provider. Waiting room time does not count. Randomization will occur via central IWRS system.

---

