### 10.4.3 ANALYSIS OF THE PRIMARY EFFICACY ENDPOINT(S)

The comparison of binary endpoints (B-lines < 15) will be performed using Chi-square or Fishers exact test, as appropriate.

Potential covariates will also be considered in a logistic regression setting to improve precision, which includes baseline co-morbidities, baseline medications (in particular guideline recommended therapies) in-hospital medications, baseline renal function, serum sodium, natriuretic peptide levels, troponin levels, renal function, baseline blood pressure, and discharge medications. Variables such as physical exam, other vital signs, and hemoconcentration may also be included. For NT-proBNP, a percent change greater than 30% and its association with the primary endpoint will be analyzed. This is based on previous work suggesting a 30% change was a key discriminatory threshold for mortality. For hemoconcentration, any increase in value in both hematocrit and hemoglobin during hospitalization will be considered positive. These covariates are known markers of risk and are standard of care assessments for the vast majority of AHF admissions. Covariates with univariately significant association with the outcome will be included together with the treatment indicator in a logistic regression model. Due to limited sample size, we will limit the number of covariates (including treatment indicator) such that there is 10 events per covariate.

---

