#### Lung Ultrasound (LUS) Protocol

To best determine the potential value of EVLW measurements using LUS, we will assess patients at multiple timepoints throughout hospitalization. (See Figure 1 – Trial design flow below)

Figure 1: Trial Schematic

For diagnostic purposes, previously published protocols have been the most well-studied.

Each LUS scan consists of 8 sectors as seen in figure 2. (Figure reproduced from Volpicelli et.al.7) Trained research personnel will record and count B-lines in each sector as visualized through one respiratory cycle at each of the time points listed in the Figure. At minimum, each stored video clip will be 6 seconds in length. The total number of B-lines for all 8 sectors will comprise the overall score. With training, the entire scan takes less than 10 minutes.

As patient positioning may impact B-lines, patients will be placed at approximately 45 degrees for all scanning. The CRF will be marked if patients are unable to lie at this angle.

- An 8 zone LUS scan will be done at the following times:
  - T00: initial LUS scan (in ED for screening and eligibility)
  - T02: 2-4 hours after initial treatment (in ED) (+/- 30 minutes)
  - T06: 2-4 hours after T02 or pre-ED discharge, whichever comes first (+/- 60 minutes)
  - HD2: 24 hours after initial scan (Day 2) (+/- 6 hours)
  - HD3: 48 hours after initial scan (Day 3) (+/- 8 hours)
  - HD4: Day 4 (anytime during day)
  - HD5: Day 5 (anytime during day)
  - HD6: Day 6 (anytime during day)
  - HD7: Day 7 (anytime during day)
- **If standard care arm do NOT notify the provider of the results**

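### Allocation is blocked within site, but the primary test ignores site; stratifying it needs no extra patients and avoids a conservative test if sites differ

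*Combined protocol and SAP*

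**What the plan says.** **Allocation.** Section 10.6.1 says "Each site will be provided a block randomization table with variable block sizes of 2, 4, and 6". One table per site means that site is a stratification factor, although the section does not use that term. The same section goes on: "We will utilize the REDCap Randomization module for web-based randomization". Section 7.3.1 names the same REDCap module in describing the web-based randomization system (IWRS), and Section 7.3.2 says "Randomization will occur via central IWRS system". No section says who holds the lists, whether site staff can see them, or that block sizes are kept from sites. On masking, Section 10.6.1 says "Due the nature of the intervention and the clinical setting, this is an unblinded trial".

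**Site units.** The Protocol Summary counts three sites with four hospitals. Section 10.2 counts four sites.

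**Primary analysis.** Section 10.4.3 says "The comparison of binary endpoints (B-lines < 15) will be performed using Chi-square", with Fisher's exact test as the alternative. A supporting logistic model takes covariates that are significant one at a time, capped so that there are ten events per covariate with treatment counted. The candidates are comorbidities, medications, laboratory values, blood pressure and clinical signs. Site is not among them.

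**Sample size.** Section 10.5 assumes 25% versus 50%, with 59 per arm, two-sided alpha 0.05 and 81% power, raised to 130 patients for drop-out.

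**The concern.** Blocking within site keeps the arms close to equal at every site, so site differences largely cancel from the treatment comparison. An unstratified test does not credit this: its standard error still contains the between-site variation. If sites differ in how many patients reach the B-line target, the test rejects less often than its nominal 5% and gives up power. In a pilot sized at 81% power there is little to spare.

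A second, smaller matter sits in the same section. Past assignments are visible at the site and the block sizes are in the protocol that site staff use, so the next assignment can be guessed better than by chance. There is some room to act on a guess: eligibility depends on more than 15 B-lines on a scan read by site research personnel, and Section 5.3 allows consented patients to become screen failures before randomization. The sentence about providing tables to sites also sits awkwardly beside central web-based assignment.

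**Working it through.** **1. The plan's power figure.** Inputs from Section 10.5: 59 per arm, 25% versus 50%, two-sided 0.05. The average rate is 0.375.
- Null SE = sqrt(2 × 0.375 × 0.625 / 59) = 0.0891.
- Alternative SE = sqrt((0.25 × 0.75 + 0.50 × 0.50) / 59) = 0.0861.
- z = (0.25 − 1.96 × 0.0891) / 0.0861 = 0.874, giving power of 80.9%.

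The stated 81% is reproduced. Exact enumeration of the uncorrected chi-square also gives 80.9%; Fisher's exact test gives 75.4%.

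**2. Why ignoring site is conservative.** Under the null, let P be the pooled binomial variance and W the average within-site variance; W equals P minus the between-site variance of the rates. With near-perfect balance within sites, the true variance of the difference is proportional to W, but the chi-square uses P. Its type I error is then about 2 × [1 − Φ(1.96 / sqrt(W/P))].

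Example with site rates of 5, 10, 35 and 50% (mean 25%):
- P = 0.25 × 0.75 = 0.1875.
- Between-site variance = (0.0400 + 0.0225 + 0.0100 + 0.0625) / 4 = 0.03375.
- W = 0.15375 and W/P = 0.82.
- 1.96 / sqrt(0.82) = 2.164, giving a type I error of 3.0%.

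**3. Simulation.** There were 20,000 trials per scenario, N = 118 in four sites of 30, 30, 29 and 29, and blocks of 2, 4 and 6 equally likely. One odds ratio common to all sites was set so that the average rates are 25% and 50%. Both tests were run on the same simulated trials. Site rates are assumed.

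| Site control rates (%) | W/P | Type I, formula | Type I, chi-square | Type I, CMH | Power, chi-square | Power, CMH | Gain (points) |
|---|---|---|---|---|---|---|---|
| 25, 25, 25, 25 | 1.00 | 5.0% | 5.1% | 4.9% | 81.4% | 81.3% | −0.1 |
| 15, 20, 30, 35 | 0.97 | 4.6% | 4.8% | 5.0% | 81.2% | 82.1% | +0.9 |
| 10, 15, 30, 45 | 0.90 | 3.9% | 4.2% | 5.3% | 82.7% | 85.7% | +3.0 |
| 5, 10, 35, 50 | 0.82 | 3.0% | 3.3% | 5.1% | 83.7% | 89.6% | +5.9 |

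CMH is the site-stratified Cochran-Mantel-Haenszel test. Simulation standard errors are about sqrt(0.05 × 0.95 / 20,000) = 0.15 points for type I error and sqrt(0.8 × 0.2 / 20,000) = 0.28 points for power. The formula runs slightly below the simulation because it assumes exact balance, whereas the last block at a site can be cut short.

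**4. Predictability.** Guessing the arm that is behind (a coin toss when level) in a complete block of size 2m is right, on average, m + (4^m / C(2m, m) − 1) / 2 times.
- Size 2: 1.5 of 2. Size 4: 2.833 of 4. Size 6: 4.1 of 6.
- Sizes 2, 4, 6 equally likely: (1.5 + 2.833 + 4.1) / 12 = 70.3%.
- On a list of 33 patients (about 130 / 4), where the last block is cut short, simulation gives 69.5%, against 50% for simple randomization.
- Without size 2, on the same basis: 68.5% for sizes 4 and 6, and 67.3% for 4, 6 and 8.
- Assignments that are certain in advance to someone who knows the sizes but not their order: 4.0% for 2/4/6, 5.7% for 4/6 and 2.3% for 4/6/8.

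**The case against.** **The unstratified test is defensible.** It is valid, simple and common in a pilot of 130 patients. The gain is at most 1 point unless sites differ widely, and nothing in the documents supports spreads of 10-45% or 5-50%. This stands: the size of the benefit is unknown. It is not a reason to keep the mismatch, because the stratified test loses essentially nothing when sites are alike.

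**Site differences in reading are limited by central review.** Section 17.3 says "Trained research personnel will record and count B-lines in each sector" at the sites, but it also describes a Core Lab that reads shuffled images blind and records the formal interpretations. The documents do not say outright which count defines the endpoint. The point therefore should not rest on reading differences between sites. Case mix and ED practice can differ by site whoever reads the images.

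**Foreknowledge is not shown.** A reader might infer from the sentence on site tables that sites can look up the next assignment. Sections 7.3.1, 7.3.2 and 10.6.1 itself all describe web-based assignment, and the natural reading is one list per site inside that system. The documents do not show that site staff hold or see the lists. What stands is a wording conflict and a missing statement of who has access.

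**Blocks of 2 are not the main problem.** A reader might infer that they are. Removing them lowers correct guessing only from 69.5% to between 67% and 69%, and sizes 4 and 6 alone make slightly more assignments certain.

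**Selection at entry would leave a trace.** Images are overread blind and screening logs record failures. That is a fair check on false counts, but it does not prevent selective approach or consent.

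**Conclusion.** The point holds as a mismatch between design and analysis. Allocation is blocked within site, while the primary test and the listed covariates leave site out. A reader might infer that the test is invalid or inflates false positives. It does not: it errs towards conservatism, with type I error falling from about 5% to about 3% as the assumed site spread widens. Stratifying restores about 5% and changes power by about 0, 1, 3 or 6 points across the four scenarios. These figures rest on assumed control rates, four roughly equal strata, a common odds ratio and equally likely block sizes, none of which the documents give.

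The concealment part is secondary. The 69.5% assumes 33 patients per list, equally likely sizes and someone who tracks every earlier assignment. It justifies withholding the block sizes and clarifying access to the lists. It does not show that assignments are known or that selection has occurred.

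**What to change.** **Section 10.4.3.** Make the primary test a Cochran-Mantel-Haenszel test stratified by site, with an exact stratified version where Fisher's test would have been used. Include site as a factor in the logistic model regardless of its univariate significance. Settle this before outcomes are examined by arm.

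**Site units.** State whether there are three or four lists, and use the same units in the analysis.

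**Events-per-covariate rule.** At the planned rates, 118 patients give 59 × (0.25 + 0.50) = about 44 events, hence four terms. Treatment plus three site indicators uses all four. Either exempt site from the count as a design factor, or fit a conditional logistic model stratified by site.

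**Section 10.6.1.** Replace the sentence on site tables with a statement that the coordinating center alone generates and holds the lists, that they are loaded in REDCap and that site staff cannot see them. Move the block sizes to a restricted document. The lists need not be regenerated merely to remove size 2.

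**Cost.** Wording and a few lines of analysis code, with no added patients. Sites that have already read the block sizes cannot unlearn them, so the last change helps only in part if enrollment is under way.

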## 11 SOURCE DOCUMENTS AND ACCESS TO SOURCE DATA/DOCUMENTS

The medical experts, study monitors, auditors, and health authority inspectors (or their agents) will be given direct access to source data and documentation (e.g., medical charts/records, laboratory test results, printouts, videotapes) for source data verification, provided that patient confidentiality is maintained in accordance with local requirements.

Each Investigator must maintain, at all times, the primary records (i.e., source documents) of each patient's data. Examples of source documents are hospital records, office visit records; examining physician's finding or notes, consultant's written opinion or notes, laboratory reports, drug inventory, study drug label records, and CRFs that are used as the source.

Each Investigator will maintain a confidential patient identification list that allows the unambiguous identification of each patient. All study-related documents must be kept for a minimum of 5 years. A publically available dataset will be released per NIH guidelines.

## 12 QUALITY ASSURANCE AND QUALITY CONTROL

*Protocol Amendments:* No changes from the final approved (signed) protocol will be initiated without the prior written approval or favorable opinion of a written amendment by the IEC/IRB, except when necessary to eliminate immediate safety concerns to the patients or when the change involves only logistics or administration. Each Investigator will sign the protocol amendment.

The IRB/EC may provide expedited review and approval/favorable opinion for minor change(s) in ongoing studies.

*Protocol Deviations, Violations, and Exceptions:* A **protocol deviation** is non-adherence to protocol-specific study procedures or schedules that does not involve inclusion/exclusion criteria, primary objective variable criteria, and/or GCP guidelines. Deviations are considered minor and do not impact the study.

A **protocol violation** is any significant divergence from the protocol, i.e., non-adherence on the part of the patient, the Investigator, or the sponsor to protocol-specific inclusion/exclusion criteria, primary objective variable criteria, and/or GCP guidelines. Protocol violations will be identified and recorded, by study center personnel.

No **exceptions** to protocol-specific entry criteria will be granted to allow patients to enter a study.

*Information to Study Personnel:* Each Investigator is responsible for giving information about the study to all staff members involved in the study or in any element of patient management, both before starting the practical performance of the study and during the course of the study (e.g., when new staff become involved). Each Investigator must assure that all study staff members are qualified by education, experience, and training to perform their specific responsibilities. These study staff members must be listed on the study center authorization form, (if required) which includes a clear description of each staff member's responsibilities. This list must be updated throughout the study, as necessary.

The study monitor is responsible for explaining the protocol to all study staff, including each Investigator, and for ensuring their compliance with the protocol. Additional information will be made available during the study when new staff become involved in the study and as otherwise agreed upon with either the Investigator or the study monitor.

The handling of data, including data quality assurance, will comply with regulatory guidelines (e.g., ICH and GCP) and the sponsor's or its designee's SOPs and working instructions. Data management and control processes specific to this study

will be described in a data management plan. When data management is outsourced, the contract organization will be responsible for the development and implementation of the data management plan.

*Data Quality Assurance:* All data on the CRF will be entered into a validated database compliant with 21 CFR Part 11 requirements. In the case when data management is outsourced, the contract organization will be responsible for database quality assurance including, but not limited to, review of data entered into the CRFs by study center personnel for completeness and accuracy and instruction of the study personnel to make any required corrections.

Data management at Indiana University will implement edit checks on the eCRF to enforce data integrity and compliance to the protocol and regulatory requirements. Study center personnel will be responsible for entering study data on the eCRFs. Data management will track eCRFs and review them for completeness, the presence of mandatory values, consistency, and dated electronic signatures. Queries identified during data discrepancy review will be sent to the study center personnel to be reviewed and resolved in a timely manner.

Adverse Events will be coded using the MedDRA dictionary. Concomitant medications will be coded using the WHO Drug dictionary. Adverse Events and Concomitant Medications will be reviewed for coding consistency and completeness.

At the end of the study, the database will be locked and the data will be released for reporting and statistical analysis.

## 13 ETHICS/PROTECTION OF HUMAN SUBJECTS

### 13.1 ETHICAL STANDARD

The Investigator(s) will conduct the study in accordance with this protocol, the guiding principles of the Declaration of Helsinki, ICH GCP guidelines and applicable regulatory requirements.

### 13.2 INSTITUTIONAL REVIEW BOARD

Before this study starts, the protocol will be submitted to each IEC/IRB for review. As required, the study will not start at a given center before the IEC/IRB for the center provides written approval or a favorable opinion. The IRB will meet all FDA requirements governing IRBs (Code of Federal Regulations, Title 21, Part 56). The IEC will meet local regulations.

### 13.3 INFORMED CONSENT PROCESS

#### 13.3.1 CONSENT/ASSENT AND OTHER INFORMATIONAL DOCUMENTS PROVIDED TO PARTICIPANTS

Each patient must be provided with a statement that the investigation involves research and that the IRB/EC has approved solicitation of patients to participate; a fair explanation of the procedures to be followed and their purposes, including identification of any procedures which are experimental; a description in lay language of any possible side effects; a description of any attendant discomforts and risks reasonably to be expected; a description of any benefits reasonably to be expected; a disclosure of any appropriate alternative procedures that might be advantageous for the patient; an offer to answer any inquiries concerning the procedures, and instruction that the person is free to withdraw consent and discontinue participation in the project or activity at any time without prejudice to the patient. The informed consent shall include a disclosure that the Investigator is being supported by the NIH to perform the stated research.

#### 13.3.2 CONSENT PROCEDURES AND DOCUMENTATION

A properly executed, written consent in compliance with current U.S. federal code 21CFR part 50, or competent regulatory authority, shall be obtained from each patient prior to entering the study or prior to performing any unusual or non-routine procedure involving risk to the patient.

A patient must give written consent to participate in the study. This consent must be dated and retained by the Principal Investigator as part of the study records. A copy shall be given to the patient. The informed consent process must be documented in the patient's source documents.

Written and/or oral information about the study in a language understandable by the patient will be given to all patients.

